Protocol

Ultrasound-guided thyroid cartilage plane block for patients with awake tracheal
intubation: a randomized controlled trial

August 29, 2023

One: Background

Traditional surface anesthesia, administered via fiberoptic bronchoscope spray, is limited by the penetration of airway secretions and local anesthetics. Excessive airway secretions can significantly compromise the effectiveness of surface anesthesia. Moreover, the vicinity of the glottis is rich in neural fibers, making the airway highly sensitive. During fiberoptic bronchoscope spray, patients often experience coughing and even laryngospasm. In contrast, thyroid cartilage plane block circumvents these limitations and offers a more precise method of airway blockage.

In recent years, both international and domestic research has focused extensively on blocking the superior laryngeal nerve. Blocking the superior laryngeal nerve can significantly reduce stimulation to the tongue base and pharynx during laryngoscopy, diminish the irritation caused by the endotracheal tube to the trachea, mitigate stress responses, and minimize adverse cardiovascular effects. This technique provides a reliable airway management method for clinical anesthesia and ICU tracheal intubation ^[1]. Research by Mathur et al. demonstrated that ultrasound-guided superior laryngeal nerve block provides effective airway anesthesia during fiberoptic bronchoscopy and reduces the incidence of adverse reactions such as coughing ^[2]. Additionally, superior laryngeal nerve block is widely applied in managing challenging airways, such as in patients with severe acute pharyngitis, cervical spine injuries,

awake tracheal intubation, percutaneous tracheostomy, laryngoscopy examinations, treatment of chronic pharyngitis, and neurogenic cough.

However, the method of performing nerve blocks through surface anatomy localization has its drawbacks, including inaccurate positioning, low success rates, poor safety, and unsatisfactory outcomes. Some researchers argue that using the thyrohyoid membrane as a target for ultrasound-guided superior laryngeal nerve block can be challenging. Traditional ultrasound-guided superior laryngeal nerve block methods often rely on the thyrohyoid membrane and the superior thyroid artery as ultrasound landmarks, injecting local anesthetic solution beneath the thyrohyoid membrane and adjacent to the superior thyroid artery. However, locating the thyrohyoid membrane and the small superior thyroid artery can be extremely challenging, especially for beginners. Even experienced clinicians, despite their familiarity with anatomy and skill, can struggle to identify these structures under ultrasound. Therefore, there is a pressing need for simpler, more precise, and easier-to-locate methods of superior laryngeal nerve block in clinical practice.

In our preliminary research, while performing superior laryngeal nerve block, we observed that the injected solution could spread along the surface of the thyroid cartilage plate, extending towards the thyrohyoid membrane. Given that the solution could reach the superior laryngeal nerve from the surface of the thyroid cartilage, we propose that injecting

local anesthetic solution on the surface of the thyroid cartilage can effectively block the superior laryngeal nerve, a technique we refer to as "Thyroid Cartilage Plane Block." This method offers the advantage of easy identification of the thyroid cartilage under ultrasound, making it more convenient to perform than traditional methods. Therefore, this study aims to investigate the clinical effectiveness and safety of superior laryngeal nerve block through surface injection of local anesthetic solution on the thyroid cartilage in patients undergoing general anesthesia with endotracheal intubation.

Two: Research Objectives

1. Primary Objective: To evaluate the effectiveness of ultrasound-guided Thyroid Cartilage Plane Block for superior laryngeal nerve blockade.
2. Secondary Objectives: To assess the safety and ease of performance of ultrasound-guided Thyroid Cartilage Plane Block for superior laryngeal nerve blockade.

Three: Research Design, Methods, and Study Steps

1. Research Design

Select patients undergoing elective awake tracheal intubation surgery and randomly assign them to two groups using a random number table. The control group will receive surface anesthesia of the throat using local anesthetic sprayed via fiberoptic bronchoscope, while the experimental group will undergo ultrasound-guided Thyroid Cartilage Plane Block.

The sample size for the study is determined based on the results of a pilot study. The primary outcome measure is the success rate of superior laryngeal nerve blockade. With a statistical power of $1-\beta=0.9$ and a significance level of $\alpha=0.05$, a sample size of $n=25$ is calculated. Assuming a dropout rate of 10%, the final sample size for each group is determined to be 30 cases.

2. Research Methods

The study will clinically evaluate the effectiveness, safety, and ease of performing Thyroid Cartilage Plane Block.

3. Study Steps

Select 60 patients undergoing elective awake tracheal intubation surgery.

Instruct patients to fast (no food or drink) for 8 hours before the procedure.

Upon admission to the operating room, monitor patients' ECG (electrocardiogram), BP (blood pressure), and SpO₂ (pulse oxygen saturation). Establish intravenous access in the upper extremities and administer normal saline solution. Administer a loading dose of dexmedetomidine at 0.5 µg/kg over 5 minutes, followed by an infusion at a rate of 0.3-0.6 µg/(kg·h) and intravenous injection of fentanyl at 0.1 µg/kg. Perform radial artery puncture and catheter placement for invasive arterial pressure monitoring. Use a computer-generated random number table to allocate patients into two groups in a 1:1 ratio. To ensure

objectivity, a nurse not involved in the study prepares sealed opaque envelopes containing the group assignments. All patients are divided into the Thyroid Cartilage Plane Block Group (T Group) and the Control Group (C Group). Patients in the C Group receive airway surface anesthesia using the fiberoptic bronchoscope-guided local anesthetic spray method throughout the procedure. In the experimental T Group, ultrasound-guided bilateral Thyroid Cartilage Plane Block is performed using the thyroid cartilage plate as an anatomical landmark. Local anesthetic is injected on the surface of the thyroid cartilage plate. The blocking procedure is as follows: Use a Sonosite high-frequency linear array transducer (5-13 MHz, Sonosite, USA). Place the transducer parallel to the spine on one side of the neck, ensuring clear visualization of the thyroid cartilage plate under ultrasound. Employ ultrasound-guided in-plane or out-of-plane techniques to display the needle insertion path and tip. Once the needle tip contacts the upper half of the thyroid cartilage plate, inject 3 ml of 2% lidocaine on the surface of the thyroid cartilage plate (the dosage is consistent with the commonly used local anesthetic volume for classic superior laryngeal nerve block methods in clinical practice). Subsequently, perform fiberoptic bronchoscope-guided oropharyngeal, subglottic, and tracheal surface anesthesia. After completing surface anesthesia, select an appropriate-sized tracheal tube and perform fiberoptic bronchoscope-guided tracheal intubation, securing

it properly.

4. The research flowchart is as follows:

Four: Patient Selection

Inclusion Criteria: We will select 60 patients who meet the following criteria for inclusion in the study:

- Patients scheduled for awake tracheal intubation surgery under general anesthesia.
- Patients with difficult airways (e.g., limited cervical spine mobility, full stomach, partial airway obstruction, craniofacial deformities or trauma, micrognathia, mouth opening <3cm, Mallampati III or IV classification) posing challenges for mask ventilation or intubation.
- Age between 18 and 65 years.
- Gender is not restricted.
- ASA classification of I or II.

Exclusion Criteria: Patients meeting any of the following criteria will be excluded from the study:

- Cardiovascular dysfunction or arterial aneurysms.
- Mental or neurological disorders or concomitant arterial aneurysms.
- Infection at the puncture site.
- Allergy to local anesthetics.
- Continuous use of antiplatelet or anticoagulant medications preoperatively.

- Hoarseness or coughing while drinking water.
- Bronchial asthma.
- Participation in other clinical trials within the previous 3 months before enrollment or current participation in other clinical trials.

3. Study Termination Criteria

The study may be terminated under the following circumstances:

- 1) Any medical condition or event occurs during the study that poses a potential risk to the continued participation of the research subjects.
- 2) Subjects receive anesthetic regimens other than the specified airway surface anesthesia rescue protocol, or if they are unable to complete the trial according to the study protocol for any reason.
- 3) The investigator determines that other circumstances warrant discontinuation from the trial.
- 4) Poor effectiveness of airway surface anesthesia, resulting in the patient's inability to tolerate awake tracheal intubation, or patient refusal to proceed.

Five: Alternative Diagnostic and Therapeutic Methods

In cases where the airway surface anesthesia is ineffective, and patients are unable to tolerate intubation, we will proceed with additional airway surface anesthesia using 2% lidocaine via a fiberoptic bronchoscope through an epidural catheter to enhance airway surface anesthesia.

Six: Assessment Parameters and Timing

Primary Outcome:

Record the comfort score immediately after intubation (5 points: resistance movement of the head or limbs; 4 points: verbal protest; 3 points: severe painful expression; 2 points: slight painful expression; 1 point: no response).

Secondary Outcomes:

1. Record the duration of the blocking procedure (from the start of ultrasound probe positioning to completion of drug administration).

2. Record the following parameters at specific time points (T0: upon entry to the operating room, T1: before insertion of the tracheal tube, T2: immediately after tracheal tube insertion, T3: 5 minutes after successful intubation):

- Mean Arterial Pressure (MAP)
- Heart Rate (HR)
- Ramsay Sedation Score (6 points: unarousable; 5 points: arousable but slow response to stimulation; 4 points: asleep but brisk response to stimulation; 3 points: asleep with a moderate response to command; 2 points: calm and cooperative with orientation; 1 point: anxious, restless, or agitated. Sedation satisfaction is defined as 2-4 points, while oversedation is defined as 5-6 points).

3. Record the number of cases with reduced voice tone before intubation.

4. Document patient coughing upon contact of the fiberoptic bronchoscope with the vocal cords before intubation (1 point: no response, 2 points: mild cough, 3 points: severe cough).
5. Assess the tolerance of the tracheal tube after successful intubation (3 points: strong resistance requiring immediate general anesthesia; 2 points: restlessness and mild resistance; 1 point: cooperative).
6. Record adverse reactions such as coughing and nausea/vomiting during intubation.
7. Document post-extubation throat pain, voice tone reduction, and voice tone reduction at 24 hours post-operation.
8. Assessment of superior laryngeal nerve blockade effectiveness based on clinical diagnostic criteria:
 - Inability to produce high-pitched sounds, monotone voice.
 - Morphological changes in the vocal cords observed during laryngoscopy (e.g., irregular vocal cord surface, wrinkles, malposition, reduced mobility).
 - Absence of neural reflex upon touching the mucosa above the vocal cords.
 - Meeting two of the above diagnostic criteria indicates successful superior laryngeal nerve blockade.
9. Record adverse reactions such as local anesthetic toxicity, local hematoma at the puncture site, and infections.

10. Record patient satisfaction.

Seven: Efficacy Assessment Criteria

- Record the duration of the blocking procedure (from the start of ultrasound probe positioning to completion of drug administration).
- Ramsay Sedation Score (6 points: unarousable; 5 points: arousable but slow response to stimulation; 4 points: asleep but brisk response to stimulation; 3 points: asleep with a moderate response to command; 2 points: calm and cooperative with orientation; 1 point: anxious, restless, or agitated. Sedation satisfaction is defined as 2-4 points, while oversedation is defined as 5-6 points).
- Patient coughing upon contact of the fiberoptic bronchoscope with the vocal cords before intubation (1 point: no response, 2 points: mild cough, 3 points: severe cough).
- Comfort score immediately after intubation (5 points: resistance movement of the head or limbs; 4 points: verbal protest; 3 points: severe painful expression; 2 points: slight painful expression; 1 point: no response).
- Tracheal tube tolerance after successful intubation (3 points: strong resistance requiring immediate general anesthesia; 2 points: restlessness and mild resistance; 1 point: cooperative).
- Assessment of superior laryngeal nerve blockade effectiveness based on clinical diagnostic criteria: nability to produce high-pitched sounds,

monotone voice.

- Morphological changes in the vocal cords observed during laryngoscopy (e.g., irregular vocal cord surface, wrinkles, malposition, reduced mobility).
- Absence of neural reflex upon touching the mucosa above the vocal cords.
- Meeting two of the above diagnostic criteria indicates excellent superior laryngeal nerve blockade effectiveness.

Eight: Observation, Recording, and Management of Adverse Events

In the event of oxygen saturation dropping below 90% during the experiment, the procedure will be halted. Patients will be instructed to take deep breaths or receive oxygen supplementation via a mask with increased pressure.

Nine: Quality Control and Quality Assurance of the Study

No specific quality control or quality assurance measures are outlined for this study.

Ten: Data Security Monitoring

Clinical research will establish an appropriate data security monitoring plan based on the level of risk. All adverse events will be meticulously documented, appropriately addressed, and tracked until resolution or stabilization. Serious adverse events and unexpected events will be reported to the ethics committee, regulatory authorities, sponsors, and

drug regulatory authorities in accordance with regulations and guidelines. The principal investigator will periodically conduct cumulative reviews of all adverse events, and if necessary, convene investigator meetings to assess the risks and benefits of the study. In double-blind trials, emergency unblinding may be performed if necessary to ensure subject safety and rights.

Eleven: Statistical Analysis

Statistical analysis will be conducted using SPSS 22.0 software. Normally distributed continuous data will be presented as mean \pm standard deviation ($\bar{x}\pm s$), and group comparisons will be made using analysis of variance (ANOVA). Categorical data will be presented as counts or percentages, and group comparisons will be made using the X^2 test. A significance level of $P<0.05$ will be considered statistically significant.

Twelve: Ethical Principles and Requirements for Clinical Research

This clinical research will adhere to ethical principles and requirements outlined in the World Medical Association's "Declaration of Helsinki" and the regulations set forth by the National Health and Family Planning Commission of the People's Republic of China, including the "Ethical Review Measures for Biomedical Research Involving Human Subjects." Specific measures will include informed consent, privacy protection, free participation in research, risk control, protection of special subjects, and

compensation for research-related harm. Prior to commencing the study, the research protocol must receive approval from the ethics committee. Before enrollment, every subject will be provided with comprehensive information about the study's purpose, procedures, and potential risks. They will sign a written informed consent form. Subjects will be informed that participation in the clinical research is entirely voluntary, and they have the right to refuse or withdraw from the study at any stage without discrimination or retaliation. Their medical treatment and rights will not be affected. Informed consent forms will be retained as part of the clinical research documents, ensuring the protection of subjects' personal privacy and data confidentiality.

References

[2] Farzi Farnoush, Haddadi Soudabeh, Ebrahimpour Neda, et al. A Survey on the Effect of Oral Gabapentin on Hemodynamic Changes During Direct Laryngoscopy and Tracheal Intubation and Intraoperative Bleeding in Patients Undergoing Septorhinoplasty. *2015*,5(5):e29705.

[3] Chen Y, Jiang C. Clinical Application Progress of Internal Branch Block of Superior Laryngeal Nerve. *Chinese Continuing Medical*

Education, 2019, 11(35): 125-127.

[4] Fowler J G, VanEenenaam Jr D P, Johnson K N, et al. Single midline injection for bilateral superior laryngeal nerve block[J]. Journal of Clinical Anesthesia, 2020, 66: 109922-109922.

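### The protocol names two different primary outcomes, block success and comfort score, and its 90% power belongs only to block success

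*Protocol*

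**What the plan says.** The protocol designates a primary outcome in two places and gives two answers.

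- **Section Three, 1. Research Design (sample size):** "The primary outcome measure is the success rate of superior laryngeal nerve blockade". The same paragraph, citing a pilot study, sets power 0.9 and alpha 0.05, obtains n=25, and with 10% dropout arrives at 30 per group.
- **Section Six, under the primary-outcome heading:** the only entry is "Record the comfort score immediately after intubation", a five-category ordinal score from 1 (no response) to 5 (resistance movement).
- **Section Six, secondary outcome 8:** "Assessment of superior laryngeal nerve blockade effectiveness based on clinical diagnostic criteria". It sets out three criteria and the rule "Meeting two of the above diagnostic criteria indicates successful superior laryngeal nerve blockade". This is the yes/no variable on which the trial was sized.

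Three other places bear on the question. Section Two gives the primary objective: "To evaluate the effectiveness of ultrasound-guided Thyroid Cartilage Plane Block for superior laryngeal nerve blockade". Section Seven lists both outcomes among the efficacy criteria without ranking them. Section Eleven sets one threshold for all comparisons: "A significance level of $P<0.05$ will be considered statistically significant".

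**The concern.** The same variable is primary in Section Three and secondary in Section Six. The two candidates are not versions of one measure. Block success is a diagnosis of nerve blockade from voice, vocal cord appearance and mucosal reflex. The comfort score grades the patient's reaction to the tube. They can give different answers.

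Two things follow. First, a sample size calculated for a success rate gives no power for a five-category ordinal score, so if Section Six governs, the declared primary outcome has no sample-size justification. Second, with two candidates and a single threshold, the protocol does not prevent the primary claim from being chosen after the results are known, and a reader could not tell which result was the pre-specified test.

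**Working it through.** **1. The passages side by side**

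| Place in protocol | Block success | Comfort score |
|---|---|---|
| Section Two, primary objective | closest fit | not named |
| Section Three, sample size | primary; n=25, 90% power | not mentioned |
| Section Six | secondary outcome 8 | sole primary |
| Section Seven | listed, unranked | listed, unranked |

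The objective favours block success, the outcome list favours the comfort score, and no statement settles it.

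**2. The plan's own figure**

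Inputs from Section Three: power 0.90, alpha 0.05, n=25, dropout 10%, 1:1 allocation. Not given: the pilot success rates and whether the test is one- or two-sided. I read n=25 as per group and assume a two-sided test.

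Dropout step: 25/(1 − 0.10) = 27.8, so 28. The stated 30 is 2 above this, which is harmless.

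Without rates, n=25 can be neither confirmed nor refuted. One can only ask which rates it fits, using the pooled two-proportion formula

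n = [1.960·√(2p̄(1−p̄)) + 1.282·√(p₁(1−p₁)+p₂(1−p₂))]² / (p₂−p₁)².

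Example, 0.50 vs 0.903: p̄ = 0.7015, so n = (1.268 + 0.745)² / 0.403² = 4.05/0.162 ≈ 25.

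| Lower rate | Higher rate giving n=25 | Difference (points) |
|---|---|---|
| near 0% | 32.5% | 32 |
| 5% | 42% | 37 |
| 10% | 50% | 40 |
| 30% | 74% | 44 |
| 50% | 90% | 40 |
| 60% | 96% | 36 |
| 67% | near 100% | 33 |

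**3. The comfort score, on assumed inputs**

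The protocol gives no distribution or effect for this score, so I assumed three control distributions over scores 1 to 5. Under proportional odds, Whitehead's formula is

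n per group = 6(1.960 + 1.282)² / [(ln OR)²(1 − Σp̄ᵢ³)], where 6 × 10.51 = 63.04.

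Example, first row at n=25: OR 5.31 gives ln OR = 1.670 and 1 − Σp̄ᵢ³ = 0.904, so n = 63.04/(2.790 × 0.904) = 25.0.

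| Assumed control distribution (%) | OR for 90% power, 25 per group | OR for 90% power, 30 per group | Probability of superiority at 30 |
|---|---|---|---|
| 20/35/25/12/8 | 5.31 | 4.58 | 0.715 |
| 10/30/30/20/10 | 5.19 | 4.50 | 0.716 |
| 40/30/15/10/5 | 6.10 | 5.13 | 0.699 |

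At 27 per group (30 less 10%) the odds ratios are 4.98, 4.88 and 5.66. Treating the score as continuous gives a similar picture: 3.242 × √(2/25) = 0.92 SD at 25 per group, and 3.242 × √(2/30) = 0.84 SD at 30.

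**4. If either outcome could carry the claim**

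Two two-sided 5% tests, with a claim made if either is significant: 1 − 0.95² = 9.75% if independent. For bivariate normal test statistics, the family-wise error is 9.1% at correlation 0.5, 7.8% at 0.8 and 5% at 1.

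**The case against.** Four points can be made on the other side.

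**A statistical analysis plan may name one primary outcome.** It may, and it was not available. But this is not a detail left for later. The protocol makes two incompatible statements, and it would still contradict itself whatever the analysis plan says.

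**The error inflation is conditional.** This stands. No passage says that success on either outcome suffices, and independence is implausible for a block meant to reduce airway stimulation and a score taken at the same intubation. The 9.75% is an upper bound on what an after-the-fact choice could do, not a property of the plan.

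**The magnitudes are illustrative.** This also stands. The score distributions are assumed. Because the control group receives spray without a nerve block, a low control success rate is at least as plausible as a moderate one, so the low-rate rows deserve equal weight. The two outcomes should also be compared at the same n, which is why 25 per group is shown for both.

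**The comfort score can be read as serving an effectiveness objective**, since Section Seven lists it as an efficacy criterion. That is arguable, although the objective names blockade of the superior laryngeal nerve, which block success measures directly.

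None of this reconciles Section Three with Section Six.

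**Conclusion.** The concern holds, and the protocol must be corrected. Section Three and Section Six each name a single primary outcome, they name different ones, and nothing decides between them. This conclusion rests on the text alone.

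The 90% power claim, whatever its inputs, relates to block success. For the comfort score the protocol supports no power figure. It does not follow that the trial is underpowered on either outcome. The ranges of 32 to 44 points for block success and odds ratios of 5.2 to 6.1 for comfort (both at 25 per group) depend on the assumed two-sided test, the per-group reading of n=25 and, for comfort, the invented distributions. They show that large effects are needed on both scales, and that a calculation for one cannot stand in for the other.

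**What to change.** Before outcome data by group are seen, name one primary outcome and bring Section Two, the sample-size paragraph in Section Three and Section Six into line with it.

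- **If block success is chosen:** list it as primary in Section Six, make the comfort score secondary, and state in Section Three the pilot success rates and the sidedness of the test behind n=25.
- **If the comfort score is chosen:** reword the primary objective so that it covers comfort, and say that n=25 and 90% power refer to block success as a secondary outcome. Withdraw the 90% claim for the primary, give the effect that 30 per group can detect with the pilot or assumed score distribution, and say whether 30 remains adequate.

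The change is to wording and adds no procedures. One outcome loses primary status. If comfort is kept, its stated power may be less favourable than 90%. Section Twelve requires ethics-committee approval of the protocol, so a change of primary outcome would presumably go through as an approved amendment.

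### The comfort score loses or masks patients in whom airway anesthesia fails: it exists only after intubation, and neither rescue nor termination for poor effect is a listed outcome

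*Protocol*

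**What the plan says.** Protocol, Section Four, 3. Study Termination Criteria, opens with "The study may be terminated under the following circumstances". Item 4 names "Poor effectiveness of airway surface anesthesia" that leads to "inability to tolerate awake tracheal intubation, or patient refusal to proceed". Item 2 gives another ground: "Subjects receive anesthetic regimens other than the specified airway surface anesthesia rescue protocol".

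Section Five deals with the same failure: "In cases where the airway surface anesthesia is ineffective, and patients are unable to tolerate intubation", then "we will proceed with additional airway surface anesthesia using 2% lidocaine via a fiberoptic bronchoscope through an epidural catheter".

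Section Six, Primary Outcome, reads "Record the comfort score immediately after intubation", on a scale from 1 (no response) to 5 (resistance movement). The scale has no level for a patient who was not intubated. Secondary outcome 5 has the same limit: "Assess the tolerance of the tracheal tube after successful intubation". Neither the ten secondary outcomes nor the criteria in Section Seven include use of rescue, abandoned awake intubation or termination for poor effect.

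**The concern.** A patient who cannot tolerate intubation because the airway anesthesia failed is the clearest treatment failure in this trial. Under the plan as written, that patient either leaves the comfort comparison or enters it with a score obtained after additional local anesthetic. Whether a score exists, and under what conditions, thus depends on how well the assigned technique worked.

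Section One argues that secretions limit sprayed anesthesia and that the block avoids this, so the protocol itself gives a reason to expect failure to differ by arm. If failures gather in the control group, scored patients understate the benefit of the block. If they gather in the block group, scored patients overstate it. Both groups receive bronchoscope-guided surface anesthesia (Section Three, 3. Study Steps), so failure and rescue can occur in either. Without counts by arm a reader cannot tell which case applies, and a later SAP cannot recover rescues that nobody recorded.

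**Working it through.** **The passages side by side**

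- Section Four, item 4: failed airway anesthesia with intubation not tolerated, or refusal. The consequence is possible termination. It is not limited to failure after rescue. I take termination to mean the subject's participation, since items 2 to 4 describe events in single subjects; that is an inference.
- Section Five: failed airway anesthesia with intubation not tolerated. The consequence is additional lidocaine.
- Section Four, item 2: the specified rescue is exempt as a ground for termination. This is the only link between the two rules. It supports rescue first but does not state it.
- Section Six: the comfort score requires intubation.

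**Size, by illustration**

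The protocol gives no failure rate or score distribution, so there is no figure of its own to reproduce on this point.

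From the protocol: 30 patients per arm, scores 1 to 5, 10% dropout.

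Assumed:
- Control (C) patients not needing rescue score 1 to 5 in proportions 20/35/25/12/8%.
- Block (T) patients not needing rescue have the same distribution, or one shifted by a proportional odds ratio (OR) of 2 in their favour.
- Failure rate f is 20% C and 5% T, or the reverse.
- Rescue comes first and succeeds in a share s of 50% or 75%.
- Rescued patients score like C patients not needing rescue. Rescue failures are not intubated.

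Means without rescue:
- C: 0.20×1 + 0.35×2 + 0.25×3 + 0.12×4 + 0.08×5 = 2.53.
- T with OR 2: the cumulative proportions 0.20, 0.55, 0.80, 0.92 become 0.333, 0.710, 0.889, 0.958, which sum to 2.890. The mean is 5 − 2.890 = 2.11.

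For an arm with mean m among patients not needing rescue:
- Scored patients only: [(1−f)m + f·s·2.53] / [1 − f(1−s)].
- Rescue failures counted as 5: (1−f)m + f·s·2.53 + f(1−s)·5.

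Example, OR 2, failure 5% C and 20% T, s = 50%:
- Scored only: C 2.53; T (0.80×2.11 + 0.10×2.53)/0.90 = 1.941/0.90 = 2.157. Difference 0.37.
- Counted: C 0.975×2.53 + 0.025×5 = 2.592; T 1.941 + 0.10×5 = 2.441. Difference 0.15.

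Mean differences, C minus T (positive favours the block):

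| Failure C / T | Patients not needing rescue | Rescue success | Scored only | Failures counted as 5 |
|---|---|---|---|---|
| 20% / 5% | identical | 50% | 0.00 | 0.19 |
| 20% / 5% | identical | 75% | 0.00 | 0.09 |
| 20% / 5% | OR 2 | 50% | 0.41 | 0.58 |
| 20% / 5% | OR 2 | 75% | 0.40 | 0.49 |
| 5% / 20% | OR 2 | 50% | 0.37 | 0.15 |
| 5% / 20% | OR 2 | 75% | 0.35 | 0.24 |

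With identical patients the gap is (f in C − f in T)(1−s)(5 − m): 0.15×0.50×2.47 = 0.19 and 0.15×0.25×2.47 = 0.09. For m from 3.5 down to 1.5 it runs from 0.15×0.50×1.5 = 0.11 to 0.15×0.50×3.5 = 0.26 at 50% success, and from 0.06 to 0.13 at 75%. With equal failure and identical patients it is zero.

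Numbers lost: 20% of 30 is 6 failures, of whom 3 (s = 50%) or on average 1.5 (s = 75%) go unscored. The dropout allowance is 10% of 30 = 3. The issue is selection, not lost precision.

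**The case against.** Four things can be said for the plan.

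- **The two rules may not conflict.** Termination is permissive, rescue is stated as what will be done, and item 2 treats rescue as part of the trial. A reader might infer a flat contradiction; the text does not support that. The flowchart announced in Section Three is not shown and may give the order. This stands: the question of order is a matter of wording.
- **The largest effects need rescue never to work.** A reader might infer that an apparent benefit could vanish. With OR 2 and failure of 5% C and 20% T, counting every failure as 5 does give −0.03, but only if no rescue succeeds. With rescue first, the benefit shrinks to 0.15 or 0.24 and remains. Likewise, 6 of 30 unscored would exceed the dropout allowance only if rescue did little. This stands, and the table above therefore uses rescue first throughout.
- **Handling may be in the SAP.** Whether non-intubated patients take the worst value is a choice about intercurrent events, and an unseen SAP may settle it. This stands against any single prescribed value. It does not answer the point about recording, because the score definition and the list of outcomes are fixed in the protocol.
- **An outcome list is not a case report form.** Terminations may be counted in ordinary participant-flow reporting, and rescue may be recorded. A reader should not infer that these data will certainly be lost. The visible text simply does not ask for them.

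Other outcomes can also still register a failure: voice change, cough before intubation and block success (Section Six, secondary outcomes 3, 4 and 8). Block success is the outcome that Section Three, 1. Research Design, calls primary.

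**Conclusion.** The concern holds for the comfort score and, by the same limit, for tube tolerance. The stated rules remove patients with failed anesthesia from the comparison, or score them after rescue, and no listed outcome shows how many there were. The distortion can run in either direction. Its true size is unknown. On the assumed rates with rescue first, counting rescue failures moves the mean difference by about 0.09 to 0.22 points on a five-point scale. It would be nil if failure were equal in the two arms and other patients were alike.

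The documents do not show that the trial as a whole is undermined. The finding rests on the visible text and on an inference about what termination means, so confidence is moderate. The change is worth making before enrolment because it is cheap and the information may not be recoverable afterwards.

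**What to change.** 1. Reconcile Section Four, item 4, with Section Five so that one event has one described path. Which path applies is for the investigator.
2. Add two yes/no fields in both arms: rescued; terminated or not intubated for poor effect. Report both by arm.
3. State that patients not intubated because of poor effect stay in the comfort comparison as treatment failures. One option is to rank them in the worst category and call the result a composite, with an analysis of scored patients alongside. The exact handling, and any sensitivity analysis for rescued patients, can be set in the SAP.

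The cost is a few sentences and two fields. There are two downsides to the composite. The worst category then mixes intolerance or refusal with observed resistance. Some power is also lost if failure is equal between arms. In a simulation on the same assumed scores (OR 2, 30 per arm, two-sided 0.05, an assumed rank test, no rescue succeeding), power falls from 30% to 26% at 5% failure per arm, from 29% to 23% at 10%, and from 26% to 16% at 20%. Successful rescues should make the loss smaller, since fewer patients then take the worst value.
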